2.3. STUDY ENDPOINTS

2.3.1. Primary Endpoints

The primary endpoints are the incidence and severity of treatment-emergent adverse events (TEAEs), serious adverse events (SAEs), and adverse events of special interest (AESIs) through Day 169/early discontinuation (ED) visit.

2.3.2. Secondary Endpoints

The secondary endpoints are:

- MOR106 serum concentrations after repeated s.c. administrations from baseline through Day 169/ED visit.
- Occurrence of ADA from baseline through Day 169/ED visit.

2.3.3. Other Endpoints

[REDACTED]

[REDACTED]

[REDACTED]

[REDACTED]

[REDACTED]

[REDACTED]

[REDACTED]

[REDACTED]

[REDACTED]

[REDACTED]

[REDACTED]

- [REDACTED]

█ [REDACTED]

[REDACTED]

█ [REDACTED]

█ [REDACTED]

█ [REDACTED]

█ [REDACTED]

█ [REDACTED]

[figure not shown]
[REDACTED]

█ [REDACTED]

█ [REDACTED]

█ [REDACTED]

2.4. SCHEMATIC DIAGRAM OF THE STUDY

R: Randomization on Day 1 (i.e. Baseline).

LD: Loading Dose (2x320 mg MOR106 or placebo) on Day 1.

*: TCS use according to approved label.

2.5. SCHEDULE OF ACTIVITIES

The study scheduled of assessments is as follows (the sections mentioned refer the protocol):

| EVENT | SCREENING PERIOD | TREATMENT PERIOD | | | | | | FOLLOW-UP PERIOD | | | | | | | |
|---|------------------|------------------|-------|----------------|--------|----------------|-----------------------------|------------------|---------------|----------------|----------------|----------------|----------------|----------------|----------------|
| | D-28 to D-7 | D1 | D4 ±1 | D15 ±2 | D29 ±2 | D43 ±2 | D57 ±2/ ETD ² | D71 ±2 | D85 ±2/ ±2 | D99 ±2 | D113 ±2 | D127 ±2 | D141 ±2 | D155 ±2 | D169 ±2/ ED |
| Study Day (D) ¹ | 1 | 2 | 3 | 4 | 5 | 6 | 7 | 8 | 9 | 10 | 11 | 12 | 13 | 14 | 15 |
| Study Visit | 1 | 2 | 3 | 4 | 5 | 6 | 7 | 8 | 9 | 10 | 11 | 12 | 13 | 14 | 15 |
| Informed consent (Section 10.4.2) | ✓ | | | | | | | | | | | | | | |
| Inclusion/exclusion criteria (Section 4.5) | ✓ | ✓ | | | | | | | | | | | | | |
| Demographics (Section 6.3) | ✓ | | | | | | | | | | | | | | |
| Medical history (Section 6.3) | ✓ | | | | | | | | | | | | | | |
| (Targeted) Physical examination (Section 6.5.3) | ✓ | ✓ | | ✓ ³ | ✓ | ✓ ³ | ✓ | ✓ ³ | ✓ | ✓ ³ | ✓ ³ | ✓ ³ | ✓ ³ | ✓ ³ | ✓ ³ |
| Vital signs (Section 6.5.4) | ✓ | ✓ | | ✓ | ✓ | ✓ | ✓ | ✓ | ✓ | ✓ | ✓ | ✓ | ✓ | ✓ | ✓ |
| Height (only at screening) and /or weight (Section 6.3) | ✓ | | | | ✓ | | ✓ | | | | | | | | |
| 12-lead ECG (Section 6.5.5) | ✓ | ✓ ⁴ | | | | ✓ ⁴ | ✓ | | ✓ | | ✓ | | | | ✓ |
| Pregnancy test ⁵ (Section 6.5.2) | ✓ | ✓ | | | ✓ | | ✓ | | | | ✓ | | | | ✓ |

¹ Visit dates are always calculated from Day 1 (unless subject discontinues early and attends an Early Treatment Discontinuation visit (ETD)). If a subject has an ETD visit, the follow-up visits are performed 14, 28, 42, 56, 70, 84, 98 and 112 days after the ETD visit.

² Subject who are discontinued from treatment during the treatment period will perform Day 57/ETD visit (14 days after the last dose) as the last visit in the treatment period before entering the follow-up period.

³ During these study visits, a targeted physical examination, consisting of cardiovascular, respiratory, gastrointestinal, and skin examination will be performed.

⁴ At Day 1, ECG to be taken before dosing (triplicate ECGs) and approximately 1 hour after dosing. At Day 43, single ECG before dosing and approximately 1h after dosing.

⁵ Females of childbearing potential only. Serum pregnancy test at screening, urine test before dosing on Day 1 and at all indicated time points thereafter.

| EVENT | SCREENING PERIOD | TREATMENT PERIOD | | | | | | FOLLOW-UP PERIOD | | | | | | | | |
|---|--|------------------|----|-------|--------|--------|--------|-----------------------------|--------|---------------|--------|---------|---------|---------|---------|----------------|
| | | D-28 to D-7 | D1 | D4 ±1 | D15 ±2 | D29 ±2 | D43 ±2 | D57 ±2/ ETD ² | D71 ±2 | D85 ±2/ ±2 | D99 ±2 | D113 ±2 | D127 ±2 | D141 ±2 | D155 ±2 | D169 ±2/ ED |
| Study Day (D) ¹ | | 1 | 2 | 3 | 4 | 5 | 6 | 7 | 8 | 9 | 10 | 11 | 12 | 13 | 14 | 15 |
| Clinical laboratory safety tests (incl. hematology, biochemistry and urinalysis), prior to injection on dosing days (Section 6.5.2) | ✓ | ✓ | | ✓ | ✓ | ✓ | ✓ | ✓ | | ✓ | | | ✓ | | ✓ | ✓ |
| Serology (Section 6.5.2) | ✓ | | | | | | | | | | | | | | | |
| ████████████████████ | ✓ | ✓ | | ✓ | ✓ | ✓ | ✓ | ✓ | ✓ | ✓ | ✓ | ✓ | ✓ | ✓ | ✓ | ✓ |
| ████████████████████ | | ✓ | | ✓ | ✓ | ✓ | ✓ | ✓ | ✓ | | ✓ | | ✓ | | ✓ | ✓ |
| Train and check compliance of e-diary use | ✓ | ✓ | | ✓ | ✓ | ✓ | ✓ | ✓ | ✓ | ✓ | ✓ | ✓ | ✓ | ✓ | ✓ | ✓ |
| ████████████████████ | Recording twice daily throughout study | | | | | | | | | | | | | | | |
| e-diary: TCS use | Recording daily throughout study | | | | | | | | | | | | | | | |
| e-diary: emollient use | Recording twice daily throughout study | | | | | | | | | | | | | | | |
| Provide Subject Participation Card (Section 10.2.4) | ✓ | | | | | | | | | | | | | | | |
| Skin swab (lesional and non-lesional) (Section 6.8.2) | | ✓ | | | | | | ✓ | | | | | | | | ✓ |
| ████████████████████ | | ✓ ⁶ | | | | | | ✓ ⁶ | | | | | | | | |

| EVENT | SCREENING PERIOD | TREATMENT PERIOD | | | | | | FOLLOW-UP PERIOD | | | | | | | |
|---|----------------------|------------------|-------|----------------|----------------|----------------|-----------------------------|------------------|---------------|--------|---------|---------|---------|---------|----------------|
| | D-28 to D-7 | D1 | D4 ±1 | D15 ±2 | D29 ±2 | D43 ±2 | D57 ±2/ ETD ² | D71 ±2 | D85 ±2/ ±2 | D99 ±2 | D113 ±2 | D127 ±2 | D141 ±2 | D155 ±2 | D169 ±2/ ED |
| Study Day (D) ¹ | 1 | 2 | 3 | 4 | 5 | 6 | 7 | 8 | 9 | 10 | 11 | 12 | 13 | 14 | 15 |
| Study Visit | | ✓ | | | | | ✓ | | | | | | | | ✓ |
| Immunogenicity assessment (ADAs; prior to injection on dosing days) (Section 6.6) | | ✓ | | | ✓ | | ✓ | | ✓ | | ✓ | | ✓ | | ✓ |
| PK blood samples (Section 6.5.6.1) | | ✓ ⁷ | ✓ | ✓ ⁷ | ✓ ⁷ | ✓ ⁷ | ✓ | ✓ | ✓ | ✓ | ✓ | ✓ | ✓ | ✓ | ✓ |
| PD and biomarker blood samples, (prior to injection on dosing days) (Section 6.7) | | ✓ | | | ✓ | | ✓ | | ✓ | | ✓ | | ✓ | | ✓ |
| Randomization (Section 4.6.1) | | ✓ | | | | | | | | | | | | | |
| IMP dosing (Section 5.2) ⁸ | | ✓ | | ✓ | ✓ | ✓ | | | | | | | | | |
| Injection site reactions (Section 6.5.6.1) | | ✓ | ✓ | ✓ | ✓ | ✓ | ✓ | | | | | | | | |
| (S)AE assessment (Sections 6.5.1, 9.2) | Throughout the study | | | | | | | | | | | | | | |
| Prior/Concomitant medications (Section 4.5.3.2) | Throughout the study | | | | | | | | | | | | | | |

⁷ PK samples have to be taken before injection and 1 hour after the injection (+/- 10 minutes) on Day 1. Samples have to be taken before injection on Days 15, 29, and 43.

⁸ A loading dose, consisting of two consecutive injections will be performed on Day 1.

3. DEFINITION OF ANALYSIS POPULATIONS

The following subject populations will be determined for this statistical analysis.

The analysis population featuring in each TLF will be printed in a subtitle.

3.1. ALL SCREENED SUBJECTS

All subjects who signed and dated an ICF and underwent screening assessments to check whether or not they are eligible to participate in the clinical study.

3.2. ALL RANDOMIZED SUBJECTS

All enrolled subjects who underwent all screening assessments and were found to be eligible for the clinical study and who were randomized into the clinical study.

3.3. SAFETY AND IMMUNOGENICITY ANALYSIS SET

All randomized subjects who received at least one dose of investigational medicinal product (IMP). This population will be named safety analysis set in the TLFs.

3.4. FULL ANALYSIS SET

All randomized subjects who received at least one dose of IMP.

3.5. PHARMACOKINETIC ANALYSIS SET

Subset of the safety set, selecting all subjects who have available and evaluable MOR106 serum concentration data (e.g. excluding all protocol deviations or AEs that may have an impact on the PK analysis).

4. TREATMENT GROUPS

Subjects being assigned to or actually receiving a common treatment during a period of time in this study, constitute a treatment group for analysis.

4.1. CONSIDERATION OF THE PLANNED VERSUS THE ACTUAL TREATMENT

The treatment group as assigned by the randomization will be used in all analyses (i.e., as-randomized analysis) except the PK analyses where the actual treatment will be used. Cross-treated subjects will be listed separately.

4.2. DEFINITION OF TREATMENT GROUP LABELS

Treatment groups will be labeled as follows over the whole statistical analysis:

- Placebo Q2W s.c.
- MOR106 320 mg Q2W s.c.

4.3. TOTALS OVER TREATMENT GROUPS

Calculation of totals over all treatment groups will be presented only in tables and only in the general subject information (e.g. baseline, prior medication, accounting) of the analysis.

5. DEFINITION OF ANALYSIS PERIODS, OF ANALYSIS TIME POINTS, AND OF BASELINE

5.1. ANALYSIS PERIODS FOR NON-VISIT DATA

These analysis periods are to be used for allocation of events into periods (e.g., adverse events).

Analyses Periods for Non-Visit Data

| Analysis period | Start period | End Period |
|---|--|---|
| Screening | Date of signing the ICF, with 00:00 added as time part. | 1 minute before the date/time of first dose of study medication* |
| Treatment | First dose of study medication date/time* | Last dose of study medication date + 30 days, with 23:59 added as time part.# |
| Follow-up | Last dose of study medication date + 31 days, with 00:00 added as time part# | Study discontinuation date, with 23:59 added as time part. |
| * For endpoints without time collected, all assessments done on the day of the first dose will be assigned to the treatment period. | | |
| # Time midnight is used as switch point to conservatively assign endpoints to the treatment period if on the date of last dose of study medication + 30 days. | | |

Note that the last analysis period in case of early discontinuation will always be ended by the study discontinuation date (date of last contact in the study).

5.2. ALGORITHM OF ALLOCATING VISITS TO TIME WINDOWS

For the efficacy, PK, PD and safety assessments, all data (including data obtained at unscheduled visits) will be placed into time windows based on the relative day (ADY) of the assessment, according to the following allocation tables:

Time windows for study drug administration:

| Time point label | Target day | Interval lower bound | Interval upper bound |
|--|------------|----------------------|----------------------|
| Day 1 | 1 | 1 | 1 |
| Day 15 | 15 | 2 | 22 |
| Day 29 | 29 | 23 | 36 |
| Day 43 | 43 | 37 | 50 |
| Day > 43 ^[1] | NA | 51 | +INF |
| [1] This time point will be only listed. | | | |

Time windows for PK:

| Time point label | Target day | Interval lower bound | Interval upper bound |
|-------------------------------------|------------|----------------------|----------------------|
| Baseline ^[1] | 1 | -INF | 1 |
| Day 1 (1h post-dose) ^[2] | 1 | 1 | 1 |
| Day 4 | 4 | 2 | 10 |
| Day 15 | 15 | 11 | 22 |
| Day 29 | 29 | 23 | 36 |
| Day 43 | 43 | 37 | 50 |
| Day 57 | 57 | 51 | 64 |
| Day 71 | 71 | 65 | 78 |
| Day 85 | 85 | 79 | 92 |
| Day 99 | 99 | 93 | 106 |
| Day 113 | 113 | 107 | 120 |
| Day 127 | 127 | 121 | 134 |
| Day 141 | 141 | 135 | 148 |
| Day 155 | 155 | 149 | 162 |
| Day 169 | 169 | 163 | 176 |
| Day > 169 ^[3] | NA | 177 | +INF |

[1] Baseline will be defined as the last measurement before the start of IMP.

[2] For Day 1 (1h post-dose), no time window is defined. The visit as recorded in the CRF will be used, time of the assessment will be used to ensure that it was done post-dose.

[3] This time point will be only listed.

Time windows for [REDACTED] vital signs and physical examination:

| Time point label | Target day | Interval lower bound | Interval upper bound |
|-------------------------|------------|----------------------|----------------------|
| Baseline ^[1] | 1 | -INF | 1 |
| Day 15 | 15 | 2 | 22 |
| Day 29 | 29 | 23 | 36 |
| Day 43 | 43 | 37 | 50 |
| Day 57 | 57 | 51 | 64 |
| Day 71 | 71 | 65 | 78 |
| Day 85 | 85 | 79 | 92 |
| Day 99 | 99 | 93 | 106 |
| Day 113 | 113 | 107 | 120 |
| Day 127 | 127 | 121 | 134 |
| Day 141 | 141 | 135 | 148 |
| Day 155 | 155 | 149 | 162 |
| Day 169 | 169 | 163 | 176 |

| Time point label | Target day | Interval lower bound | Interval upper bound |
|--------------------------|------------|----------------------|----------------------|
| Day > 169 ^[2] | NA | 177 | +INF |

[1] Baseline will be defined as the last measurement before the start of IMP.
[2] This time point will be only listed.

Time windows for weight:

| Time point label | Target day | Interval lower bound | Interval upper bound |
|-------------------------|------------|----------------------|----------------------|
| Baseline ^[1] | 1 | -INF | 1 |
| Day 29 | 29 | 2 | 43 |
| Day 57 | 57 | 44 | 71 |
| > Day 57 ^[2] | NA | 72 | +INF |

[1] Baseline will be defined as the last measurement before the start of IMP.
[2] This time point will be only listed.

Time windows for ECG:

| Time point label | Target day | Interval lower bound | Interval upper bound |
|--------------------------------------|------------|----------------------|----------------------|
| Baseline ^[1] | 1 | -INF | 1 |
| Day 1 (1h post-dose) ^[2] | 1 | 1 | 1 |
| Day 43 (pre-dose) ^[3] | 43 | 2 | 50 |
| Day 43 (1h post-dose) ^[2] | 43 | 2 | 50 |
| Day 57 | 57 | 51 | 71 |
| Day 85 | 85 | 72 | 99 |
| Day 113 | 113 | 100 | 141 |
| Day 169 | 169 | 142 | 176 |
| > Day 169 ^[4] | NA | 177 | +INF |

[1] Baseline will be defined as the last measurement before the start of IMP.
[2] 1h post-dose assessment, no time window is defined. The visit as recorded in the CRF will be used, time of the assessment will be used to ensure that it was done post-dose.
[3] Pre-dose assessment, no time window is defined. The visit as recorded in the CRF will be used, time of the assessment will be used to ensure that it was done pre-dose.
[4] This time point will be only listed.

Time windows for safety laboratory tests:

| Time point label | Target day | Interval lower bound | Interval upper bound |
|-------------------------|------------|----------------------|----------------------|
| Baseline ^[1] | 1 | -INF | 1 |
| Day 15 | 15 | 2 | 22 |
| Day 29 | 29 | 23 | 36 |
| Day 43 | 43 | 37 | 50 |
| Day 57 | 57 | 51 | 71 |
| Day 85 | 85 | 72 | 106 |

| Time point label | Target day | Interval lower bound | Interval upper bound |
|--------------------------|------------|----------------------|----------------------|
| Day 127 | 127 | 107 | 141 |
| Day 155 | 155 | 142 | 162 |
| Day 169 | 169 | 163 | 176 |
| > Day 169 ^[2] | NA | 177 | +INF |

[1] Baseline will be defined as the last measurement before the start of IMP.
[2] This time point will be only listed.

Time windows for [REDACTED]

| Time point label | Target day | Interval lower bound | Interval upper bound |
|--------------------------|------------|----------------------|----------------------|
| Baseline ^[1] | 1 | -INF | 1 |
| Day 15 | 15 | 2 | 22 |
| Day 29 | 29 | 23 | 36 |
| Day 43 | 43 | 37 | 50 |
| Day 57 | 57 | 51 | 64 |
| Day 71 | 71 | 65 | 85 |
| Day 99 | 99 | 86 | 113 |
| Day 127 | 127 | 114 | 141 |
| Day 155 | 155 | 142 | 162 |
| Day 169 | 169 | 163 | 176 |
| > Day 169 ^[2] | NA | 177 | +INF |

[1] Baseline will be defined as the last measurement before the start of IMP.
[2] This time point will be only listed.

Time windows for pregnancy test:

| Time point label | Target day | Interval lower bound | Interval upper bound |
|--------------------------|------------|----------------------|----------------------|
| Baseline ^[1] | 1 | -INF | 1 |
| Day 29 | 29 | 2 | 43 |
| Day 57 | 57 | 44 | 85 |
| Day 113 | 113 | 86 | 141 |
| Day 169 | 169 | 141 | 176 |
| > Day 169 ^[2] | NA | 177 | +INF |

[1] Baseline will be defined as the last measurement before the start of IMP.
[2] This time point will be only listed.

Time windows for [REDACTED]

| Time point label | Target day | Interval lower bound | Interval upper bound |
|-------------------------|------------|----------------------|----------------------|
| Baseline ^[1] | 1 | -INF | 1 |
| Day 57 | 57 | 2 | 64 |
| > Day 57 ^[2] | NA | 65 | +INF |

[1] Baseline will be defined as the last measurement before the start of IMP.
[2] This time point will be only listed.

Time windows for immunogenicity (ADA), PD and biomarkers:

| Time point label | Target day | Interval lower bound | Interval upper bound |
|--------------------------|------------|----------------------|----------------------|
| Baseline ^[1] | 1 | -INF | 1 |
| Day 29 | 29 | 2 | 43 |
| Day 57 | 57 | 44 | 71 |
| Day 85 | 85 | 72 | 99 |
| Day 113 | 113 | 100 | 127 |
| Day 141 | 141 | 128 | 155 |
| Day 169 | 169 | 156 | 176 |
| > Day 169 ^[2] | NA | 177 | +INF |

[1] Baseline will be defined as the last measurement before the start of IMP.
[2] This time point will be only listed.

Time windows for injection site reactions:

| Time point label | Target day | Interval lower bound | Interval upper bound |
|-------------------------|------------|----------------------|----------------------|
| Day 1 | 1 | 1 | 1 |
| Day 4 | 4 | 2 | 10 |
| Day 15 | 15 | 11 | 22 |
| Day 29 | 29 | 23 | 36 |
| Day 43 | 43 | 37 | 50 |
| Day 57 | 57 | 51 | 64 |
| Day > 57 ^[1] | NA | 65 | +INF |

[1] This time point will be only listed.

Time windows for skin swab:

| Time point label | Target day | Interval lower bound | Interval upper bound |
|---|------------|----------------------|----------------------|
| Baseline ^[1] | 1 | -INF | 1 |
| Day 57 | 57 | 2 | 113 |
| Day 169 | 169 | 114 | 176 |
| > Day 169 ^[2] | NA | 177 | +INF |
| [1] Baseline will be defined as the last measurement before the start of IMP. | | | |
| [2] This time point will be only listed. | | | |

Tables and figures will present the time points, not the visits. Listings will display the time points as recorded in CRF and as derived per the above time windows.

5.3. SELECTION OF VISITS

In case there are multiple measurements within a post-baseline time window, the one closest to the target day will be selected for the analyses. If there are multiple measurements at the same distance of the target day (meaning: equal $ABS[ADY - \text{target day}]$), then the one latest in time will be selected. If multiple measurements are taken on the same day, the mean of these values will be used. All data will be presented in listings with a flag if they were used in the analysis.

5.4. CALCULATION OF RELATIVE DAYS AND DURATIONS

The timing of an assessment or event (start or stop) relative to a referential date will be calculated as follows:

$ADY (\text{day}) = \text{concerned date} - \text{reference date} (+ 1 \text{ day only when the concerned date is the same or later than the reference date})$

Where:

- ADY is the analysis relative day count;
- *Concerned date* is an assessment visit date, or the start or stop date of an event;
- *Date* implies a complete date (day, month and year available);
- *Reference date* default is the date of first administration of study drug, unless otherwise specified.

Provided the resolution of the inputs (and respective unit) are adapted, the general terms of this formula also apply when similar relative timings are required in another time resolution, like in minutes.

Durations will be calculated in a similar way as:

$\text{Duration (days)} = \text{end date} - \text{start date} + 1.$

5.5. DEFINITION OF BASELINE

For each individual parameter, the last available result before the date and time of first study drug administration, whichever this assessment is, constitutes the reference assessment, i.e. baseline.

For electrocardiogram (ECG), the baseline is defined as the mean of the last recorded triplicate before the first study drug administration. If no triplicate is available before the first dose of study medication intake, the last ECG value will be considered as baseline.

6. SELECTION OF DATA RECORDS FOR ANALYSIS

All reported events, and all assessments without missing results will be used in the statistical analysis. However, the next specific exclusions will be done in some specific applications.

6.1. RECORDS HAVING EXTREME VALUES

Records yielding extreme results will be used for analysis in the general subject information, efficacy and safety parts of the analysis, even when these results are unusual or seemingly impossible.

In the PK/ part of the analysis, exclusion of abnormal PK concentration results/ will be formally discussed and determined after data base lock and before running the PK analysis, and documented in the PK/ Data Review Report.

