4.3.3. Other Endpoints

4.4. Potential Risks and Benefits

No risk factors for clinical use of MOR106 were identified based on the mode of action of the antibody (i.e. IL-17C antagonism). Two relevant nonclinical species were identified (mouse and cynomolgus monkey). Toxicity studies in these species applied a multiple of the doses anticipated for human use whereas no systemic drug-related AEs were observed (i.e. NOAEL in each nonclinical safety study defined at the highest dose studied) (Manciaux, 2016a), (Manciaux, 2016b), (Perron, 2017), and (Grote-Wessels, 2018). S.c. administration of MOR106 in cynomolgus monkeys did also not reveal any relevant observations of local intolerance during a 4-week period of time, up to 300 mg/kg. No sign for treatment-related immunotoxicity and no risk for a cytokine release syndrome became apparent during the study. Nevertheless, potential reactions will be monitored in this clinical study.

Data on the biology of the target IL-17C (a member of the IL-17 cytokine family) indicates a role of IL-17C as a regulatory cytokine for innate immune function in epithelial cells.

By neutralizing the biological activity of human IL-17C, MOR106 may have the potential of providing benefit as an effective and safe long-term treatment. This is in comparison to current oral immunosuppressants and glucocorticoids that are only approved as short-term or intermittent therapies, because their long-term use is restricted by concerns over toxicity and side effects.

The FIH study, MOR106-CL-101, has not identified any safety risks for i.v. administered MOR106 up to 20 mg/kg single doses. One healthy subject exhibited transient ADA development without any effect on PK and without impact on clinical safety findings.

In the FIH study MAD part i.v. administered MOR106 was well tolerated with no identified safety risks at doses up to four weekly doses of 10 mg/kg. One subject with moderate to severe AD developed a positive ADA titer during the follow-up period exhibiting clearing effects on the PK. There was no impact of the ADA formation on safety of this subject. The results from the exploratory objectives in the FIH study in terms of efficacy support the potential of MOR106 in the treatment of moderate to severe AD. The risk of immunogenicity will be thoroughly monitored throughout the trial.

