16. APPENDIX

16.1. PK DATA REVIEW

For the review of PK/ data, following items should be checked:

- I. PK
 - I.1. MISSING PK DATA
 - I.1.1. Missing concentrations/measurement
 - I.2. REVIEW OF PK PROFILES AND CONCENTRATION VALUES
 - I.2.1. Abnormal PK concentration/measurement profiles
 - I.2.2. Abnormal PK concentration/measurement data point
- II. PK ANALYSIS SET
- II. PK ANALYSIS SET

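### MOR106 concentrations can be excluded as abnormal after database lock with no assignable cause required, so genuine ADA-driven low levels could drop out of the only PK summary table; a conflicting BLOQ rule removes cleared late values in any case

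*SAP*

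**What the plan says.** The first secondary endpoint (SAP 2.3.2) is "MOR106 serum concentrations after repeated s.c. administrations from baseline through Day 169/ED visit". The second is the occurrence of ADA over the same span.

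SAP 6.1 treats extreme values in two ways. In the general subject information, efficacy and safety parts they stay in, "even when these results are unusual or seemingly impossible". In the PK part, exclusion of abnormal concentration results "will be formally discussed and determined after data base lock and before running the PK analysis", with the decision recorded in a data review report. Appendix 16.1 lists what that review checks: missing data, "Abnormal PK concentration/measurement profiles" and "Abnormal PK concentration/measurement data point". Neither place says what makes a value or a profile abnormal.

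SAP 3.5 builds the PK analysis set by "excluding all protocol deviations or AEs that may have an impact on the PK analysis", as Protocol 7.2.6 already did. Table 14.2.2.1 and all three PK listings use that set.

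On immunogenicity, Protocol 4.4 reports two cases from the first-in-human study: "One subject with moderate to severe AD developed a positive ADA titer during the follow-up period exhibiting clearing effects on the PK", and "One healthy subject exhibited transient ADA development without any effect on PK".

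On values below quantification, SAP 7.8 imputes 0 for descriptive statistics and LLOQ/2 for the geometric mean and geometric CV. SAP 11.1.3 refers to that rule, then adds that BLOQ values after the last quantifiable concentration are set to missing. It does the same for embedded BLOQ values after the Day 43 dose.

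**The concern.** An exclusion rule based on how a value looks, applied once the data are locked, selects on the outcome being summarised. In this programme a low profile need not be an error, because ADA-driven clearance is a real effect of giving the antibody. Protocol 4.2.2 gives watching for ADA after treatment stops as one reason for the 16-week follow-up.

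Table 14.2.2.1 is the only tabulated PK summary, and population PK is reported separately. The ADA table does not cross ADA status with concentration. If a cleared profile were excluded, no planned table would show the exposure loss. Mean exposure would be overstated and its spread understated, mainly at the later visits, since the reported clearing case became ADA-positive during follow-up.

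The original reason for cleaning profiles has also weakened: SAP 11.1.2 derives no PK parameters and SAP 8.2.1 drops the half-life, so no non-compartmental fit needs protecting.

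**Working it through.** **Inputs from the documents.** The MOR106 arm has n = 40 (Protocol 7.1). One PK-clearing ADA case and one ADA case without PK effect are reported (Protocol 4.4).

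**Assumed inputs.** The documents give no ADA rate, size of clearing or between-subject CV for this trial. I take k = 1, 2 or 4 cleared subjects of 40, levels at a fraction f of the others (0 to 0.5), and CV 30%.

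**The plan's own figure.** Protocol 7.1 gives an 87% chance of seeing at least one event of 5% incidence among 40: 1 − 0.95^40 = 0.871, which reproduces. The same formula gives the chance of at least one ADA-cleared profile: 1 − 0.975^40 = 64% at a 2.5% rate and 1 − 0.90^40 = 98.5% at 10%.

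**Arithmetic mean if k cleared subjects are dropped.** The ratio without to with them is 1 / (1 − (k/n)(1 − f)).

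| k of 40 | f = 0 | f = 0.5 |
|---|---|---|
| 1 | +2.6% | +1.3% |
| 2 | 40/38: +5.3% | +2.6% |
| 4 | 40/36: +11.1% | +5.3% |

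If evaluability falls evenly across arms (51/60 × 40 = 34), the f = 0 results for k = 2 and 4 become 34/32 = +6.2% and 34/30 = +13.3%.

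**Geometric mean.** The ratio is f^(−k/n). With one of 40 subjects at 1% of the others, 0.01^(−1/40) = 1.122, or +12.2%. With two subjects it is +25.9%.

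**Spread.** With a share q = k/n at zero and CV c in the rest, the CV including the zeros is √[(1 + c²)/(1 − q) − 1]. At c = 0.30:
- q = 0.05: √(1.09/0.95 − 1) = 38%.
- q = 0.10: √(1.09/0.90 − 1) = 46%.

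Dropping the zeros returns 30% in both cases.

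**Opposite direction.** Dropping one high value at 3 times the others (assumed) gives 1/(1 + 2/40) − 1 = −4.8%.

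**BLOQ rules side by side.** A subject cleared below quantification at the late visits contributes 0 under SAP 7.8 and nothing under SAP 11.1.3. With b such subjects of n, the arithmetic means differ by n/(n − b), so b = 2 or 4 again gives 5.3% or 11.1%. The factor also grows with ordinary washout. At the point where half the subjects are quantifiable, just short of where SAP 7.3 restricts the statistics, it is 40/20 = 2. SAP 7.3 further provides for a calculated mean below the LLOQ. At late visits that can hardly arise if terminal BLOQ values have been removed, so SAP 7.3 appears to presume the SAP 7.8 rule.

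**The case against.** The safeguards are real. The decision comes before the PK analysis, is written up in a report, and excluded data are flagged in the outputs. The ADA table and listing use the safety set, so PK exclusions cannot touch the ADA endpoint. This stands, but it gives transparency rather than a criterion. The PK listings also use the PK analysis set, so a subject removed from it has no concentrations shown there. Listing 16.2.1.3 would show set membership only.

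Three stronger readings are tempting and are not supported:
- **The plan will delete ADA-cleared profiles.** SAP 6.1 and 16.1 name abnormal data as matters for review. They do not direct removal, single out low values or mention ADA. The documents report one clearing subject, and the other ADA case had no PK effect.
- **The bias must be upward.** That holds only if low values are the ones dropped.
- **The AE clause in SAP 3.5 removes ADA-positive subjects.** ADA positivity is not defined as an AE, and Protocol 4.4 says ADA did not affect that subject's safety.

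The size is also modest. At CV 30% and n = 40 the standard error is 30%/√40 = 4.7% of the mean, so a 5.3% shift is about one standard error. Development in atopic dermatitis had already been stopped for futility (SAP 1). Finally, SAP 6.1 and 16.1 show gaps and the PK SOPs cited in SAP 7.9.2 are not available, so the absence of a cause requirement is established only for the visible text.

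**Conclusion.** The point holds as a gap that could distort the PK summary, not as a prediction that it will. In the visible text, MOR106 values and whole profiles may be excluded for looking abnormal, after database lock and without an assignable cause. ADA-driven clearance is a documented way for a valid profile to look abnormal.

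If 2 or 4 near-zero subjects of 40 were dropped, the arithmetic mean would be overstated by 5.3% or 11.1% and the CV understated. The geometric mean is more sensitive. These sizes rest on assumed rates and depths of clearing.

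The BLOQ conflict is the more definite defect. SAP 11.1.3, as written, removes fully cleared late values whatever is decided under SAP 6.1, and it contradicts SAP 7.8. Both matters affect description only: the endpoint carries no test, so type I error and power are untouched.

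**What to change.** - **SAP 6.1, 3.5 and 16.1:** permit exclusion only for a documented sampling, dosing, handling or bioanalytical error, and never for magnitude or ADA status alone.
- **Table 14.2.2.1:** run it on all valid concentrations with ADA-positive subjects flagged. Show any version with further exclusions as a sensitivity table.
- **Listings:** list subjects left out of the PK analysis set, with the reason and their concentrations.
- **SAP 11.1.3:** for the descriptive concentration summaries, apply the SAP 7.8 imputation in place of the set-to-missing rules.

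The cost is a few sentences, a somewhat wider descriptive spread and at most one extra table. No new data are needed.
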